## **I. Research Objectives/Background**

Over 15 million Americans living with Alzheimer's disease and other dementias (AD/D) receive daily care from family caregivers (unpaid individuals, typically but not always related, who assume responsibility for daily care and decision-making). Caring for a person living with dementia (PLWD) greatly alters caregivers' daily lives, often resulting in depression and anxiety as they labor throughout the illness trajectory. Caregiving challenges typically increase as the patient nears death. Family caregivers of PLWD often lack support during their most active caregiving and into bereavement. This situation intensifies both caregiving-related distress and caregivers' grief.

Caregivers' pre-bereavement experience is associated with how well they adapt to their post-loss lives. Caregivers who experience pre-bereavement depression, anxiety, and inadequate social support are likely to experience more intense grief and distress after their loved one dies. Thus, interventions that reduce caregivers' pre-bereavement depression and anxiety may improve the caregiving experience and bereavement journey.

Hospice is one of the few healthcare services that follow caregivers into bereavement. Although Medicare Conditions of Participation require hospice agencies to deliver bereavement services, no standards exist to prescribe how these services are delivered. Furthermore, many hospice agencies lack resources to provide comprehensive services to all bereaved caregivers. Current efforts for supporting hospice caregivers of PLWD show little efficacy at reducing pre- and post-loss depression and anxiety during caregiving and into bereavement. We propose a randomized controlled trial (RCT) of a technologically-mediated, storytelling intervention, Caregiver Speaks. Caregiver Speaks empowers caregivers' self-expression, moderated by increased social support, to make meaning of the caregiving and bereavement experiences, thus reducing depression and anxiety.

Park and Folkman's meaning-making coping model posits that an individual's ability to make sense of, and find benefit in, an adverse life situation (e.g., caregiving and bereavement) will be enhanced by social support, resulting in reduced depression, anxiety, and grief intensity. Caregiver Speaks will employ photo-elicitation – using photos to elicit caregivers' thoughts and feelings about their experiences – and a private Facebook (FB) group to enable them to capture and share their stories with one another in a supportive online environment. The overarching goal of this application is to determine the efficacy of Caregiver Speaks in reducing depression

and anxiety among hospice family caregivers of people with end-stage AD/D. Our specific aims, qualitative research questions, and quantitative hypotheses are as follows:

Specific Aim 1: Determine the efficacy of the Caregiver Speaks intervention in reducing depression and anxiety among hospice family caregivers of PLWD.

Research Question (RQ) 1: What is the effect of the Caregiver Speaks intervention on caregivers' depression, anxiety (outcomes of interest)?

Hypothesis (H) 1a: Family caregivers receiving the intervention will report lower levels of depression and anxiety (outcomes of interest), which is facilitated by higher social support (mediating variable) than those in the control group during active caregiving.

H1b: Family caregivers receiving the intervention will report lower levels of depression and anxiety (outcomes of interest), which is facilitated by higher social support (mediating variable) than those in the control group during bereavement.

H1c: Among the intervention group, family caregivers with higher baseline depression scores will experience a larger reduction in depression compared to those with less depression at baseline.

Specific Aim 2: Examine the effect of the Caregiver Speaks intervention on grief intensity among bereaved hospice family caregivers of PLWD.

H2: Bereaved family caregivers receiving the intervention will report lower grief intensity (outcome of interest) than those in the control group.

Specific Aim 3: Describe how caregivers make meaning of their caregiving and bereavement experiences.

RQ 2: In what ways do active caregivers find meaning as reflected in their FB posts?

RQ 3: In what ways do bereaved caregivers find meaning as reflected in their FB posts?

RQ 4: In what ways does social validation in an online group facilitate meaning making?

A two-arm multi-site RCT with a mixed-methods analysis will examine the efficacy of a photo-elicitation intervention to reduce caregiver anxiety and depression (Aim 1-2).

Qualitative methods will provide insight into how the intervention works to enhance meaning-making and improve caregiver outcomes (Aim 3).

Sub-Study:

RQ: How are sibling relationships shaped by caring for a parent with dementia?

RQ2: How are sibling relationships shaped by parental death and bereavement in the context of dementia?

**REDCap Referral and Consent Database Changes as of 9/7/2021:**

- Indicator (yes/no) will be added to the consent form that denotes whether or not the intervention ‘teach back’ was included during the consent process.
- Caregivers will be asked about other family members who might be interested in participating in the study, a notes field will be included so that this information can be added.
- Indicator (yes/no) will be added to the referral form to indicate if the Medical Record (MRN) for the patient was thoroughly searched. A notes field will also be added so that additional MRN info can be noted.
- Indicator (yes/no) added to account for caregivers who initially consent, but subsequently are removed as consents because they did not fill out the baseline and ignored staff contact or opted out of participating when. If ‘yes’ is indicated, a notes field is triggered so that the reason for removal can be added as well.

### **REDCap Referral and Consent Changes as of 6/16/2022:**

- When making the initial recruitment call, two questions will be added as a digital literacy screening. If the referral scores 6 or lower on either of the digital literacy screening questions, an alternate recruitment script will be utilized emphasizing the technological assistance the research team can provide to participants.
- Digital literacy screening questions:
  - On a scale of 1-10 with 1 being poor and 10 being excellent, how do you rate your overall skills with technological devices such as cell phones, computers?
  - On a scale of 1-10 with 1 being poor and 10 being excellent, how do you rate your overall skills with social media applications such as Facebook?

### **IV. Inclusion/Exclusion Criteria**

Participants must 1) be a designated family caregiver (i.e., a family member or friend providing unpaid care) of a PLWD who is enrolled in hospice care, 2) be at least 18 years old, 3) be involved in decisions related to their loved one’s hospice care, 4) have access to a digital camera or other photo-taking device such as a cell phone, 5) be willing to photograph images they feel capture their caregiving and bereavement experiences, 6) be willing to set up a Facebook account and join the private Facebook group, and 7) have access to e-mail for REDCap survey data collection. Family caregivers without an internet-enabled device will be given a smart phone and data plan restricted to Facebook use for the duration of their participation in the study.

### **V. Number of Subjects**

1. The anticipated enrollment number is 468 subjects (or 234 for intervention group and 234 for control).
2. The PHQ-9 is widely used, has good internal consistency, is well validated, and is commonly used to inquire about the degree to which an individual has experienced depressed mood over the past two weeks. Our power calculations based on our preliminary work hold the following assumptions: 1) attrition rate of 30% 2) 80% power

3) a two-sided alternative for group differences at the 0.05 level of significance for a change in PHQ-9 scores (average of 4 points, variance of 5.5).

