## VI. Study Procedures/Study Design

**Group 1: Usual care.** Participants in this group will receive standard hospice care and bereavement support according to the policy of each hospice agency. We considered using an attention match control but chose “usual care” instead, as prior research demonstrated that using attention match control in a behavioral randomized trial is problematic, especially for outcomes such as depression (our primary outcome of interest) and anxiety. This literature advocates that controlling for attention is not necessary and counterproductive in some behavioral intervention trials. Once assigned to an arm, the participant remains in that arm for the entire study, from active caregiving through bereavement. We will not randomize a second time at bereavement. Control group participants will complete study measures electronically through the REDCap system at the same intervals as the intervention group.

**Group 2: Caregiver Speaks intervention group.** Participants in this group will receive usual care plus the Caregiver Speaks intervention. They will participate in a Facebook group to share their photos and personal stories. During the initial zoom meeting, a research staff person will 1) train caregivers how to set-up and use Facebook, if needed, 2) discuss elements of their story and identify artifacts they may wish to feature in their photo-elicitation process, and 3) enroll them in the pre-bereavement caregiver private Facebook group. Caregivers will participate in this group until the PLWD dies, at which time they will transition (one month) into a bereavement focused group. The bereavement group will include the same components, but the focus of the photos and conversation will be on bereavement. Table 1 provides a summary of the study and intervention participation, as well as the data collection schedule. We will provide caregivers a printed reference guide for using Facebook, including group rules and common Facebook terms, based on materials we have used extensively in our preliminary work.

In an effort to increase retention of participants, the interventionist will now add a follow-up/technical assistance phone call with each NEW intervention participant after they have completed one full week of the intervention to assess the following:

- a. whether or not there are barriers to accessing/using Facebook.
- b. whether or not caregivers are able to share photos.

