### **Data Analysis Plan:**

**Statistical Assumptions.** We will examine linearity and homoskedasticity by calculating and plotting residuals and Cook's distance for all models. Where data are missing, we will use the Last Observation Carried Forward (LOCF) missing data imputation technique, given that < 30% of data were missing for any particular subject in our prior work. If the proportion of missing data is higher, we will use regression based multiple imputation. Little's MCAR test (missing completely at random) will be used to test that missingness is in no way related to the intervention. Because the sample size is relatively large, we expect that known and unknown confounders will be distributed evenly among the two randomized groups. Additional confounders will only be introduced as covariates if we find evidence of imbalance between groups at baseline. We acknowledge that this study is not powered to detect small interaction effects.

We will test whether randomization created balanced groups by comparing baseline measures and demographic characteristics, using chi-square or t-test analysis for categorical or continuous variables, respectively. Variables that differ significantly between groups will be included in regression models as potential confounders. We will include time from study enrollment to the last observation as a covariate, as well as hospice agency. We will report estimates with 95% confidence intervals. To draw inferences from our study for the likely benefit to an equivalent population, where the intervention under trial is a model of service delivery, all analyses of outcomes will be by intention-to-treat. The intention-to-treat analysis, consistent with the objectives of a pragmatic trial, will minimize the influence of "informative missingness" of the data and preserve groups' comparability.

**Statistical Analysis.** H1a: Family caregivers receiving the intervention will report lower levels of depression and anxiety (outcomes of interest), which is facilitated by higher social support (mediating variable) than those in the control group during active caregiving.

H1b: Family caregivers receiving the intervention will report lower levels of depression and anxiety (outcomes of interest), which is facilitated by higher social support (mediating variable) than those in the control group during bereavement.

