# **Caregiver Speaks Data Analysis Plan**

**January 5, 2019**

**NCT04103580**

## Data Analysis

### Statistical Assumptions

We will routinely test assumptions of linearity, independence and homoskedasticity by calculating and plotting residuals and Cook's distance for all models. Where data are missing, we will substitute the mode for categorical data and the median for continuous data, given that <0.5% of data were missing for any measure in our preliminary trial. If the proportion of missing data is higher, we will use multiple imputation. In the analysis for H1a, we will use the final measure provided by caregiver before patient death, and for H1b we will use the final measure during bereavement. Because the sample size is relatively large, we expect that known and unknown confounders will be distributed evenly among the two groups. We acknowledge that this study is not powered to detect small interaction effects. Additional confounders will only be introduced as covariates if we find evidence of imbalance between groups at baseline.

We will test whether randomization created balanced groups by comparing baseline measures and demographic characteristics, using chi-square or t-test analysis for categorical or continuous variables, respectively. Variables that differ significantly between groups will be included in regression models as potential confounders. To compare outcomes for our hypotheses, we will use the last available measure post-baseline and prior to death or the end of the study and last measure during bereavement. This is a last-observation analysis.

Carpenter and Kenward argue that, in such analyses, time to this event should be taken into account. Therefore, we will include time from study enrollment to the last observation as a covariate. We will report estimates with 95% confidence intervals. To draw inferences from our study to the likely benefit to an equivalent population where the intervention under trial is a model of service delivery, all analyses of outcomes will be by intention-to-treat. The intention-to-treat analysis, consistent with the objectives of a pragmatic trial, will minimize the influence of "informative missingness" of the data and preserve groups' comparability.

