### Statistical Analysis

**H1a:** Family caregivers receiving the Caregiver Speaks intervention will report lower levels of depression and anxiety compared to those in the control group during active caregiving.

**H1b:** Family caregivers receiving the intervention will report lower levels of depression and anxiety compared to those in the control group during bereavement.

**H2:** Bereaved family caregivers receiving the intervention will report lower levels of grief intensity compared to those in the control group.

We will examine differences between longitudinal profiles of the two study groups for each of the outcomes (PHQ-9, GAD-7, social support, & grief intensity). We will use mixed (hierarchical) models with repeated outcome measures nested within participants (see model below). This will allow us to draw inferences about how our outcome measures (PHQ-9, GAD-7 & grief intensity) change over time (slope) between the two study groups. Mixed models are able to accommodate differing numbers of measurements at varying time intervals for participants. Additionally, we will examine how social support mediates our outcomes of interest (depression, anxiety, and grief intensity). As described above, we will also include covariates where indicated.

**Last post-baseline measure =  $\beta_0 + \beta_1[\text{study group}] + \beta_2[\text{baseline measure}] + \beta_3[\text{time since enrollment}]$**

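### PHQ-9 is the single primary outcome but is compared between arms in two phases, with one stated 0.05 and no primary phase, testing order, alpha split or success rule

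*Protocol*

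**What the plan says.** **One primary outcome.** Protocol section VI, in explaining the choice of control, justifies usual care "especially for outcomes such as depression (our primary outcome of interest) and anxiety". Table 2 of the same section lists PHQ-9 as primary, and GAD-7 and TRIG-Present as secondary.

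**One significance level.** Protocol section V gives the power assumptions, which include "a two-sided alternative for group differences at the 0.05 level of significance for a change in PHQ-9 scores". No phase or time point is attached; the size of the change is put at "average of 4 points, variance of 5.5". The Data Analysis Plan in section VI adds "We will report estimates with 95% confidence intervals", and the SAP says the same.

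**Two phase-specific hypotheses.** H1a in the SAP (Statistical Analysis) reads "Family caregivers receiving the Caregiver Speaks intervention will report lower levels of depression and anxiety compared to those in the control group during active caregiving". The matching statement for bereavement is H1b. The Protocol carries the same pair under Specific Aim 1.

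**Two endpoints.** The SAP (Statistical Assumptions) takes, for H1a, the caregiver's last assessment while the patient is alive, and "for H1b we will use the final measure during bereavement".

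**What is absent.** Neither document gives a primary phase, an order of testing, a division of alpha, a multiplicity adjustment, or a statement of what result would count as success on Aim 1.

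**The concern.** Specific Aim 1 is to determine efficacy on depression and anxiety. With two PHQ-9 comparisons and no rule joining them, a significant result in either phase could be presented as meeting that aim, and the phase to be stressed could be chosen after the results are known. A reader who sees one primary outcome and one 0.05 would assume that a false positive on the primary question has a 5% chance. Under an either-phase reading it is higher.

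**Working it through.** **Inputs.** Two-sided alpha 0.05 (Protocol section V). Two PHQ-9 comparisons (H1a and H1b; SAP, Statistical Assumptions and Statistical Analysis). One randomisation covers both phases and participants stay in their arm (Protocol section VI, Group 1), so the two test statistics are probably positively correlated. The correlation is not given, so a range is assumed.

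**The plan's own figure.** Section V states 468 in total for 80% power. The usual two-mean formula, n per arm = 2(1.960 + 0.842)² × variance / difference², gives 2 × 7.85 × 5.5 / 16 = 5.4, so 6 per arm, or 12 in total and 18 after 30% attrition. Reading 5.5 as a standard deviation gives 2 × 7.85 × 30.25 / 16 = 29.7, so 30 per arm, or 60 in total and 86 after attrition. Neither reproduces 468. That is a separate matter. It means only that the power figures below take the stated design as having 80% power at 0.05, without endorsing it.

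**Error if either phase suffices.** With no effect in either phase, the chance of at least one rejection is 1 − P(|Z1| ≤ 1.96 and |Z2| ≤ 1.96). For independent tests this is 1 − 0.95² = 0.0975. For correlated tests it comes from the bivariate normal distribution. The right-hand column counts only false findings of benefit, 1 − P(Z1 ≤ 1.96 and Z2 ≤ 1.96), for which a single test has 0.025.

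| Assumed correlation | Two-sided error | Ratio to 0.05 | False benefit only |
|---|---|---|---|
| 0 | 0.0975 | 1.95 | 0.0494 |
| 0.3 | 0.0951 | 1.90 | 0.0476 |
| 0.5 | 0.0907 | 1.81 | 0.0454 |
| 0.7 | 0.0835 | 1.67 | 0.0417 |
| 0.8 | 0.0781 | 1.56 | 0.0390 |

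The independence value is the ceiling. Caregivers with data in only one phase pull the correlation down, so values near the top of the table cannot be excluded.

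**Error if both phases are required.** Both tests must reject. Under independence with no effect in either phase, the chance is 0.05² = 0.0025. Whatever the correlation, it cannot exceed 0.05.

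**Error under a fixed order.** If the first null hypothesis is true, any false claim requires the first test to reject, which has probability 0.05. If it is false, only the second test can err, again at 0.05. The family-wise error is therefore at most 0.05.

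**Cost of an alpha split instead.** At 0.025 per phase the error is 1 − 0.975² = 0.0494 if the tests are independent. A comparison with 80% power at 0.05 falls to Φ(2.802 − 2.241) = Φ(0.560) = 0.71. Keeping 80% multiplies the sample size by (2.241 + 0.842)² / (1.960 + 0.842)² = 1.21, so 468 becomes about 567.

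**The case against.** The best defence is that H1a and H1b are separate hypotheses, each confined to its phase. If each result is claimed only for its own phase, controlling error per hypothesis is a common position, and if both are needed there is nothing to correct. This stands as far as it goes: the documents do not adopt an either-phase rule. But they do not adopt any other rule either, and Aim 1 is a single efficacy aim on a single primary outcome, so the gap remains.

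A reader might go further in several ways that the documents do not support.

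- *That each phase is assigned 0.05, or that the trial promises a 5% family-wise rate.* The 0.05 appears once, as a sample-size assumption. Unadjusted 95% intervals fit a 0.05 test per phase but do not set a decision rule.
- *That the false-positive rate is in fact nearly doubled.* That is the independence ceiling, and it also needs the either-phase rule. With the same randomised caregivers in both phases, a somewhat lower figure is likely.
- *That 9.75% is the rate of false efficacy claims.* The hypotheses are directional, and a rejection showing harm would not be reported as efficacy. The rate of false benefit is about 3.9% to 4.9%, against 2.5% for one test.
- *That adding GAD-7 in both phases (1 − 0.95⁴ = 18.5%) and grief intensity (1 − 0.95⁵ = 22.6%) measures error on the primary claim.* Table 2 already labels those outcomes secondary.

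It is also fair to say that the count of two endpoints comes from the SAP. The Protocol's model equation has one slope per arm and no phase term. The Protocol nevertheless states both phase-specific hypotheses, so it does not reduce the comparison to one.

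**Conclusion.** The concern holds as an unspecified success rule for the primary outcome. PHQ-9 has two phase-specific comparisons, one stated alpha with no phase attached, and nothing to say how they combine. If either phase may support the Aim 1 claim at 0.05, the two-sided family-wise error is at most 9.75%, and about 7.8% to 9.5% for correlations of 0.8 to 0.3. This rests on three assumptions: that either phase suffices, that each is tested at 0.05, and that the correlation lies in that range. The first is the one the documents leave open, and a both-required rule would remove the inflation. The correction is cheap and changes what the trial may conclude, so it is worth making.

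**What to change.** Before outcomes are examined by arm, amend the SAP to designate one phase's PHQ-9 comparison as the primary test at two-sided 0.05, and to test the other phase's PHQ-9 at 0.05 only if the first is significant. Keep GAD-7 and TRIG-Present as secondary outcomes, reported with intervals.

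The choice of order is the sponsor's, since the documents do not rank the phases. H1a first is one reasonable choice: it comes first in time, and some caregivers will not reach bereavement (Protocol section IX provides for this at wind-down). It should not be justified by saying that every enrolled caregiver contributes. The first follow-up is at day 14 (Table 2), so a death before then may leave no post-baseline measure for H1a.

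**Cost.** A few lines of SAP text and no change in sample size. The first test keeps its 0.05. Because section V names no phase, nothing more can be said about the stated power. The downside is that the second phase cannot be formally claimed if the first test fails. If each test had a nominal 80% power, the chance of claiming both would be 0.8 × 0.8 = 64% under independence, and higher with positive correlation. A 0.025 split avoids that dependence, but lowers a nominal 80% power to about 71% per phase. A both-required rule also controls the error, but neither phase can then carry the claim alone.
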